9.3 Secondary Efficacy Analyses

9.3.1 Evaluation of Response

Investigator assessments as reported on electric case report forms (eCRFs) will be used to identify confirmed response as described in Section 8.1. The overall irRC/ irRECIST response categories are: Complete Response (irCR), Partial Response (irPR), Stable Disease (irSD), Progressive Disease (irPD), and Not Evaluable (irNE). The overall RECIST v1.1 response categories are: Complete Response (CR), Partial Response (PR), Stable Disease (SD), Progressive Disease (PD), and Not Evaluable (NE). If any post-baseline scheduled tumor assessment is missed, that visit-level response for that visit will be 'Not Done'.

The ORR, DRR, and DCR will be estimated by the MLE for secondary response endpoints. The MLE is $\hat{p} = s_1/n_1$ if the arm stops after Stage 1 and $\hat{p} = (s_1+s_2)/(n_1+n_2)$ otherwise, where s_i =the number of subjects with a response in Stage i and n_i =number of subjects in stage i, $i=1,2$. All secondary response rate endpoints will be summarized descriptively by treatment arm for phase 2 subjects with the number of subjects with a response, percentage, and exact two-sided 95% CIs.

The number and percent of subjects in each of the best overall tumor response categories, using irRECIST and RECIST v1.1, will be summarized for phase 2 subjects. Exact two-sided 95% confidence intervals will be provided for each best overall tumor response category by treatment arm.

Durable response rate (DRR) is defined as the proportion of subjects experiencing CR or PR by RECIST v1.1 (irCR or irPR by irRECIST) lasting approximately 6 months continuously and beginning within 12 months of the first dose of study treatment. The length of durable response is calculated as $((\text{Date of Documentation of Death or Disease Progression} - \text{Date of First Objective Response} + 1) / 30.4375)$.

The DRR using irRECIST and RECIST v1.1 will be summarized descriptively by treatment arm for phase 2 subjects with the number of subjects, percentage, and exact two-sided 95% CIs.

Disease control rate (DCR) using irRECIST and RECIST v1.1 will be summarized descriptively by treatment arm for phase 2 subjects with the number of subjects, percentage, and exact two-sided 95% CIs.

Swimmers' lane plots will also be produced showing time to response (RECIST v 1.1), duration of response, type of response, and duration of treatment for the phase 2 results.

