8.6 Interim Analysis

There are 3 interim and 1 final analyses planned:

- A planned analysis of phase 1 results at the completion of dose escalation for both combinations will be conducted.
- An analysis of the safety and efficacy results in each phase 2 arm will be conducted separately after 21 subjects in the primary efficacy population (used in the two-stage design) have had at least 2 post-baseline disease assessments.
- The final analysis by efficacy populations of all subjects in the IMO-2125 + ipilimumab arm will be done when all subjects have had at least 2 post-baseline disease assessments.

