9.3.2 Evaluation of Time to Event Endpoints

The OS and PFS proportions will be estimated at 6 and 12 months; OS and PFS will also be analyzed overall with Kaplan-Meier estimate including median. For time-to-event endpoints (OS, PFS, and DoR), the Kaplan-Meier method will be used to estimate the probability of event-free survival. The analyses of OS, PFS, and DoR will only be done for the subjects treated at the RP2D for each treatment arm.

Kaplan-Meier plots will be produced for OS and PFS by treatment arm. Subgroup analysis of overall survival at 6 and 12 months, as well as progression-free survival, may be performed for the 8 mg IMO-2125 and ipilimumab combination dose group if data supports it.

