	14.3.6.3	Vital Signs – CTCAE Shift from Baseline (Safety Population)
14.3.7		Electrocardiogram
	14.3.7.1.1	Electrocardiogram – Overall Interpretation (Safety Population)
	14.3.7.1.2	Electrocardiogram – Overall Interpretation Shift from Baseline (Safety Population)
	14.3.7.2.1	Electrocardiogram – Abnormal QTcF Results (Safety Population)
	14.3.7.2.2	Electrocardiogram – QTcF Shift from Baseline (Safety Population)
14.3.8		ECOG Performance Status
	14.3.8.1	ECOG –Shift from Baseline (Safety Population)

Efficacy Phase 2

ICH Heading	Table Number	Table Description
14.2		EFFICACY Analyses
	14.2.1.1.1a	Best Overall Response, ORR, Durable Response Rate, and Disease Control Rate – RECIST v1.1 (PIIEE and/or PPIEE Populations)
	14.2.1.1.1b	Best Overall Response, ORR, Durable Response Rate, and Disease Control Rate – RECIST v1.1 (PIIEE and SIIIE Populations)
	14.2.1.1.2	Best Overall Response, ORR, Durable Response Rate, and Disease Control Rate – RECIST v1.1 (SIIIE Population)
	14.2.1.2.1a	Best Overall Response, ORR, Durable Response Rate, and Disease Control Rate – irRECIST (PIIEE and/or PPIEE Populations)
	14.2.1.2.1b	Best Overall Response, ORR, Durable Response Rate, and Disease Control Rate – irRECIST (PIIEE and SIIIE Populations)
	14.2.1.2.2	Best Overall Response, ORR, Durable Response Rate, and Disease Control Rate – irRECIST (SIIIE Population)
14.2.2		Tumor Response – Subgroup Analysis
	14.2.2.1.1.1a	Best Overall Response, ORR, Durable Response Rate, and Disease Control Rate by Subgroups of Interest – RECIST v1.1 (PIIEE and/or PPIEE Populations)
	14.2.2.1.1.1b	Best Overall Response, ORR, Durable Response Rate, and Disease Control Rate by Subgroups of Interest – RECIST v1.1 (PIIEE and SIIIE Populations)
	14.2.2.1.1.2	Best Overall Response, ORR, Durable Response Rate, and Disease Control Rate by Subgroups of Interest – RECIST v1.1 (SIIIE Population)
	14.2.2.1.2.1a	Best Overall Response, ORR, Durable Response Rate, and Disease Control Rate by Subgroups of Interest – irRECIST (PIIEE and/or PPIEE Populations)
	14.2.2.1.2.1b	Best Overall Response, ORR, Durable Response Rate, and Disease Control Rate by Subgroups of Interest – irRECIST (PIIEE and SIIIE Populations)

ICH Heading	Table Number	Table Description
	14.2.2.1.2.2	Best Overall Response, ORR, Durable Response Rate, and Disease Control Rate by Subgroups of Interest – irRECIST (SIIIE Population)
14.2.3		Survival, PFS, and Duration of Response
	14.2.3.1a	Overall Survival (OS) (PIIEE and/or PPIEE Populations)

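### The durable response rate has no rule for ongoing responses and no exact threshold, and the listed analyses can fall before late-enrolled responders could reach 6 months

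*SAP*

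**What the plan says.** Section 9.3.1 of the SAP defines DRR as the proportion of subjects with CR or PR "lasting approximately 6 months continuously and beginning within 12 months of the first dose of study treatment". "The length of durable response is calculated as" the date of death or progression minus the date of first objective response, plus 1, divided by 30.4375. The section then says: "The ORR, DRR, and DCR will be estimated by the MLE for secondary response endpoints". That estimate is responders over all subjects, and the rate is reported with an exact two-sided 95% CI.

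Section 8.4 gives a censoring rule for PFS and DoR, and allows no imputation beyond what that section describes. Section 8.5 extends the PFS censoring rules to DoR. Neither section names DRR.

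On timing, Section 8.6 says: "There are 3 interim and 1 final analyses planned". One is the Phase 1 analysis. For Phase 2, "An analysis of the safety and efficacy results in each phase 2 arm will be conducted separately after 21 subjects" in the primary efficacy population have at least two post-baseline disease assessments. The final analysis, listed for the ipilimumab arm only, "will be done when all subjects have had at least 2 post-baseline disease assessments". Appendix E places DRR in the same tables as the other response rates: "Best Overall Response, ORR, Durable Response Rate, and Disease Control Rate".

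**The concern.** A responder who has neither died nor progressed has no end date, so the formula gives no length, even after eight or ten months of response. These are the responses the endpoint is meant to count. DRR is a proportion, so each subject must be classed as durable or not, and no rule does this for an ongoing response. The word approximately leaves the threshold open as well.

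Timing adds a second problem. A 6-month endpoint is tabulated at a cut that can come about two months after the last subjects' first scan. Those subjects cannot yet be durable, but they stay in the denominator. The exact CI reflects sampling error and does not show short follow-up. DRR is a named Phase 2 secondary endpoint (Section 2.2), and both open choices would be settled after data are seen.

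**Working it through.** The SAP states no DRR follow-up figure, so there is none to reproduce.

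**Inputs.** Scans are at Weeks 8, 17 and 29, each ±7 days, then at least every 3 months; confirmatory scans are at least 4 weeks after first documentation (Section 3.4, Table 5 footnotes). The study ends about 1 year after the last Phase 2 subject starts (Section 3.2.2). Assumption: the first scan after Week 29 is 13 weeks later, at Week 42.

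**Observed length, measured to the scan**, as (days + 1)/30.4375. The SAP formula gives no value for an ongoing response, so using the scan as the end point is my convention.

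| Onset to scan | Days | Months |
|---|---|---|
| Week 8 to 17 | 63 | 64/30.4375 = 2.10 |
| Same, with scan windows | 49 to 77 | 1.64 to 2.56 |
| Week 8 to 12 (confirmatory scan is the second assessment) | 28 | 29/30.4375 = 0.95 |
| Week 17 to 17 | 0 | 1/30.4375 = 0.03 |
| Week 8 to 29 | 147 | 148/30.4375 = 4.86 |
| Week 8 to 42 | 238 | 239/30.4375 = 7.85 |
| Week 17 to 42 | 175 | 176/30.4375 = 5.78 |
| Same, with Week 17 window | 168 to 182 | 5.55 to 6.01 |

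Six months is 6 × 30.4375 = 182.6 days, or 26.1 weeks. At the minimum cut no last-enrolled responder is near it. The Week 17 to 42 rows show why the threshold wording matters: 5.78 months passes or fails depending on what approximately means.

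**Who is too early at the cut.** On this grid the first scan that can show about 6 months is Week 42. The cut is at the last subject's Week 17, so anyone who started less than 42 − 17 = 25 weeks before that subject is too early. If scans are more frequent, the limit for a Week 8 onset is 8 + 26.1 − 17 = 17.1 weeks. For a Week 17 onset it is 26.1 weeks.

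**Effect on DRR.** Accrual is not in the SAP. I assume uniform accrual, a true DRR of 20%, and that an ongoing response counts once it is seen at the threshold. DRR then reads 20% × (1 − share too early).

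| Accrual | Share, 25 weeks | DRR reads | Share, 17.1 weeks (Week 8 onsets) | DRR reads |
|---|---|---|---|---|
| 12 months (52.2 weeks) | 0.479 | 10.4% | 0.328 | 13.4% |
| 18 months (78.3 weeks) | 0.319 | 13.6% | 0.218 | 15.6% |
| 24 months (104.4 weeks) | 0.239 | 15.2% | 0.164 | 16.7% |

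Section 3.1.2 lets Phase 1 subjects treated at the RP2D contribute. If 3 to 8 of the 21 are such subjects with full follow-up (assumed), the 25-week shares fall to between 0.479 × 18/21 = 0.411 and 0.239 × 13/21 = 0.148, and DRR reads 11.8% to 17.0%.

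In counts, 4/21 (19.0%, exact 95% CI 5.4 to 41.9) could read 3/21 (14.3%, 3.0 to 36.3) or 2/21 (9.5%, 1.2 to 30.4).

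**Effect of the missing rule alone.** Suppose 6 of 21 respond and all are ongoing (assumed). DRR is 0/21 (0 to 16.1%) if a response without a length is not durable, and 6/21 (28.6%, 11.3 to 52.2) if every ongoing response counts.

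**Feasibility at study end.** At about Week 52 the last subject's follow-up is 309/30.4375 = 10.15 months from Week 8 and 246/30.4375 = 8.08 months from Week 17. The Week 42 scan is available to everyone. An onset at Week 29 would need 29 + 26.1 = 55.1 weeks, so late onsets in the last subjects remain out of reach.

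**The case against.** The best defence is that DRR classifies the DoR variable. The two formulas use the same dates apart from the plus 1, and DoR has a full censoring rule, so a cross-reference would close the gap. That helps with the length but not with the classification: a censored duration of 2.1 months still does not say whether the subject is durable.

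A second defence concerns timing. Two assessments is a minimum, most of the listed analyses are called interim, and DRR is not tied to any one of them. Section 8.5 mentions a data cut-off for study closure, and Section 9.3.2 says "The OS and PFS proportions will be estimated at 6 and 12 months", which needs longer follow-up than Week 17. A reader might infer that DRR will never be reported on mature data. The document does not support that, because later data are planned and a later report is possible. What stands is that Section 8.6 ties no analysis to study end and lists none after the 21-subject analysis for pembrolizumab.

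Third, the bias figures rest on assumed accrual, an assumed true rate and my rule for ongoing responses. That is correct, and they are conditional. The direction is firmer: counting a two-month ongoing response as durable would contradict the definition, so any reading that respects it leaves late enrollees as non-durable.

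Finally, the Kaplan-Meier DoR analysis and the swimmer plots do show ongoing responses. They soften the consequence but do not give the DRR.

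**Conclusion.** The point holds. Applied as written at the minimum cut, the rule counts responders who are ongoing or too recent as not durable, and the threshold can be chosen after the data are seen. The loss is about 5 to 10 percentage points from an assumed 20% on the sparsest grid, about 3 to 7 points for Week 8 onsets with more frequent scans, and less if well-followed Phase 1 subjects contribute. All of these rest on assumed uniform accrual over 12 to 24 months.

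Three stronger readings should be avoided. The 2.1 months is not typical of all responders: it is the on-schedule maximum for a last-enrolled Week 8 onset, and earlier enrollees have more. A halved DRR is only the 12-month, sparse-grid end of the range. The first 21 ipilimumab subjects will also have longer follow-up at that arm's final analysis. Lastly, the trial's primary conclusion is not affected, because DRR is descriptive and the ORR test does not use it. The change should be made, but it concerns one secondary endpoint.

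**What to change.** 1. In Section 9.3.1, state that a responder without progression or death counts as durable if an assessment before any new anti-cancer therapy shows continued response at or beyond the threshold. Align the handling of new therapy with the DoR rule, which censors on the date the new therapy starts, and use one day-count convention (the DoR formula omits the plus 1), so that one responder does not have two lengths.
2. Set the threshold in days, with a stated scan-window allowance. Say whether a Week 17 onset still in response at about Week 42 (about 175 days) passes.
3. Add to Section 8.6 an analysis of DRR for both arms at study end, about 1 year after the last subject starts. At any earlier cut, give the number of responders not yet followed long enough.

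A 6-month Kaplan-Meier estimate of DoR beside DRR would be a useful but optional supplement.

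The cost is SAP wording, a later reporting date for one descriptive endpoint and slightly more analysis work. The follow-up scans are already planned.

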9.3.2 Evaluation of Time to Event Endpoints

The OS and PFS proportions will be estimated at 6 and 12 months; OS and PFS will also be analyzed overall with Kaplan-Meier estimate including median. For time-to-event endpoints (OS, PFS, and DoR), the Kaplan-Meier method will be used to estimate the probability of event-free survival. The analyses of OS, PFS, and DoR will only be done for the subjects treated at the RP2D for each treatment arm.

Kaplan-Meier plots will be produced for OS and PFS by treatment arm. Subgroup analysis of overall survival at 6 and 12 months, as well as progression-free survival, may be performed for the 8 mg IMO-2125 and ipilimumab combination dose group if data supports it.

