2.2 Secondary Objectives

The secondary objectives of Phase 1 are to determine the plasma pharmacokinetics (PK) of single-dose IMO-2125 and repeat-dose IMO-2125 PK administered intratumorally in combination with ipilimumab and pembrolizumab. An additional secondary objective of Phase 1 is to describe any preliminary antitumor activity.

The secondary objectives of Phase 2 are to further assess the safety and tolerability of IMO-2125 in combination with ipilimumab or in combination with pembrolizumab in subjects with metastatic melanoma and to assess treatment response using RECIST v1.1 and irRECIST, overall survival (OS), OS at 6 months and 12 months, progression-free survival (PFS), PFS at 6 months and 12 months, durable response rate (DRR), duration of response (DoR), and disease control rate (DCR).

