3. STUDY DESIGN AND PLAN

3.1 Overview

This is a two arm open-label Phase 1/2 study to assess the safety, tolerability, PK, immunogenicity, and efficacy of IMO-2125 when administered in combination with ipilimumab or in combination with pembrolizumab. Subjects with metastatic melanoma who have experienced symptomatic or confirmed radiographic progression to their most recent treatment regimen (anti-PD-[L]1 alone or in combination) will be eligible. Prior BRAF or MEK inhibitor treatment is not required. The study will be conducted in two parts: a dose-escalation portion (Phase 1) to evaluate safety and tolerability of multiple dose levels and a Phase 2 portion to assess preliminary efficacy.

3.1.1 Phase 1

The Phase 1 portion of the study is will explore escalating dose levels of IMO-2125 (from 4 to 32 mg with de-escalation to 2 mg allowed for each IMO-2125 combination). For each cohort, IMO-2125 will be administered as a once-weekly intratumorally injection for 3 consecutive weeks in Cycle 1, followed by intratumorally injections on Weeks 5, 8, 11, 17, 23, and 29 (Day 1 of Cycles 2 through 7). Both ipilimumab and pembrolizumab will be administered as per the USPI every 3 weeks beginning Day 1 of Week 2. Continued dosing of pembrolizumab following the study treatment period is permitted at the discretion of the Investigator for subjects in the IMO-2125 + pembrolizumab treatment arm. The dosing schedule is summarized in Table 1.

Table 1: Schedule of Dosing for Phase 1 and Phase 2

	Cycle															
	1				2			3			4			5	6	7
Study week	1	2	3	4	5	6	7	8	9	10	11	12	13	17	23	29
IMO-2125 + ipilimumab																
IMO-2125	X	X	X	-	X	-	-	X	-	-	X	-	-	X	X	X
Ipilimumab	-	X	-	-	X	-	-	X	-	-	X	-	-	-	-	-
IMO-2125 + pembrolizumab																
IMO-2125	X	X	X	-	X	-	-	X	-	-	X	-	-	X	X	X
Pembrolizumab	-	X	-	-	X	-	-	X	-	-	X	X ¹				

Note: On weeks when the combinations are administered, administration of ipilimumab or pembrolizumab will be first, followed by IMO-2125. IMO-2125 administration must occur within a ±2 day window of the scheduled dosing day.

¹ For subjects in the IMO-2125 + pembrolizumab treatment arm, continued pembrolizumab dosing per the approved product label is permitted at the discretion of the Investigator

Subjects assigned to 11 weeks of IMO-2125 under previous versions of the protocol who have not yet reached the end of the Treatment Period may receive the Week 17, 23, and 29 injections at the discretion of the treating Investigator.

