3.2.2 Study Duration and Study Completion

The study ends approximately 1 year after the last subject in Phase 2 has commenced study treatment. Subjects who complete or discontinue study treatment prior to progression will be followed for clinical and radiological evidence of progression and immunogenicity assessment at least every 3 months until documentation of RECIST v1.1 progressive disease (PD), start of a subsequent anti-cancer treatment regimen, withdrawal of consent, death, or Sponsor notification that follow-up is no longer required, whichever comes first. Best response to first subsequent therapy, AEs which are Grade ≥ 3 , and concomitant medications used to treat these AEs, will also be captured during the follow-up phase of the study (Table 4 and Table 5).

After documentation of PD or use of a subsequent anti-cancer treatment regimen, all subjects will be contacted by telephone every 3 months for a survival follow-up until the site is notified by the Sponsor that survival follow-up is no longer required. A subject has completed the study at the earliest of death or study end.

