⁹ CBC with differential should be done 24 to 48 hours after the IMO-2125 injection, to coincide with the post-injection biopsy (if the biopsy is conducted). Chemistry profile and coagulation tests do not have to be conducted if Screening tests were conducted within 7 days of the Cycle 1 Week 1 Visit.

¹⁰PT, aPTT, INR.

¹¹ Blood pressure, heart rate, respiratory rate, and temperature.

¹² Week 2 ECG pre-dose and at 2 hours post-IMO-2125 administration. Week 11 ECG at 2 hours post-IMO-2125 administration.

¹³ Including assessment of melanoma lesions.

¹⁴ In Phase 2, all tumor biopsies are optional. See Section 13.2 of the protocol and the Laboratory Manual for details on the collection of biopsies and analyses of biomarkers.

¹⁵ Biopsy of the injected tumor should occur within 24 to 48 hours after injection (no more than 48 hours).

¹⁶ In Phase 2, blood biomarker samples will be collected from at least 20 patients treated at the IMO-2125 RP2D after which the Sponsor will determine if additional samples are needed. The blood biomarker samples will be collected on Day 1 before IMO-2125 administration, 4 hours after IMO-2125 administration, and 24 to 48 hours (coinciding with the 24-hour PK sample) after the injection. At Week 2 and Cycle 3 Week 8, collect before ipilimumab or pembrolizumab dosing.

¹⁷ Radiologic assessment and Investigator assessment of response at Week 8, Week 17, and Week 29 may be conducted within a \pm 7-day window.

¹⁸ At least every 3 months until progression, start of next melanoma treatment, withdrawal of consent, death, or Sponsor notification that follow up is no longer required.

¹⁹ In Phase 2, response assessed using irRECIST and RECIST v 1.1. Best response to first subsequent treatment should also be captured. Confirmatory scans for CR, PR, and progressive disease should be performed \geq 4 weeks after the date the response was first documented.

²⁰ To minimize bias in the PRO data, the PRO assessments should be completed before study drug administration and AE assessments.

²¹ For patients assigned to the IMO-2125 + pembrolizumab treatment arm, continued pembrolizumab dosing per the approved product label is permitted at the discretion of the Investigator.

²² PK: blood sampling for analysis of plasma concentrations of IMO-2125 and serum concentrations of ipilimumab, and pembrolizumab (See **Error! Reference source not found.**Table 3 of the protocol for specific collection

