8.5 Efficacy Endpoints

ORR is defined as the proportion subjects with a best confirmed overall response of complete response (CR) or partial response (PR), with assessment of response to be determined by the investigator using irRECIST and RECIST v1.1.

OS is defined as the number of months from initiation of treatment to death from any cause. Subjects who have not died at their last contact will be censored on the date of last contact. The specifications for the time to death calculation are:

- If death is reported either on AE or Death CRF pages, OS will be calculated as *Date of Documentation of (Death – First Dose Date + 1) / 30.4375*.
- Subjects will be censored at their last contact date if death is not reported at the data cut-off date for study closure, and their survival time will be calculated as *(/Last Contact Date - First Dose Date + 1) / 30.4375*). Last contact date is defined as the last date reported among, Adverse Event (AE start date), the Study Exit Status, Hematology, Chemistry, Assessment of RECIST v1.1 Response, Assessment of irRECIST Response, Long Term Follow Up, Study Drug Administration (IMO-2125), ipilimumab Infusion and pembrolizumab Infusion pages of the eCRF.
- Subjects lacking data after the date of first dose who do not die will have their survival time censored on the date of first dose with duration of 1 day.

PFS, defined as number of months from the initiation of treatment to disease progression using RECIST v1.1 or irRECIST or death from any cause, will be calculated as *([Date of Documentation of Death or Disease Progression – First Dose Date + 1]/30.43750*. Subjects without reported progression at their last contact date will be censored on the date of their last valid disease assessment. A valid disease assessment is any disease assessment with overall visit-level response of irCR irPR, irSD, or irPD (without subsequent confirmation) when using irRECIST and CR, PR, or SD when using RECIST v1.1. Subjects who start new anti-cancer therapy before a PFS event will be censored on the date of initiation of new anti-cancer therapy (Subsequent Anti Cancer Therapy eCRF page).

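### 6-month PFS is estimated before the Week 29 scan can occur, so progression first found at that scan counts as progression-free and the estimate is biased upward

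*SAP*

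**What the plan says.** PFS at these landmarks is a named Phase 2 secondary objective: section 2.2 lists "progression-free survival (PFS), PFS at 6 months and 12 months". Section 9.3.2 states that "The OS and PFS proportions will be estimated at 6 and 12 months" and that "the Kaplan-Meier method will be used to estimate the probability of event-free survival".

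Section 8.5 gives the endpoint: "PFS, defined as number of months from the initiation of treatment to disease progression using RECIST v1.1 or irRECIST or death from any cause". The event date is the date on which death or progression is documented. Days are counted from first dose, plus 1, and divided by 30.4375. Subjects without progression are censored at their last valid disease assessment.

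The scan calendar is in section 3.4. The Phase 2 table footnote reads "Radiologic assessment and Investigator assessment of response at Week 8, Week 17, and Week 29 may be conducted within a" window of 7 days either side. After that the footnote for follow-up radiology says "At least every 3 months until progression, start of next melanoma treatment, withdrawal of consent, death", or sponsor notice. Section 3.2.2 adds that "Subjects who complete or discontinue study treatment prior to progression will be followed for clinical and radiological evidence of progression", at the same maximum interval.

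The SAP has no landmark window, no interval-censored analysis and no caveat linking the landmarks to the scan dates.

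**The concern.** When progression is dated at the scan that shows it, a Kaplan-Meier PFS curve falls mainly at scan times. A landmark just before a scheduled scan misses the progression that the scan is about to reveal. Month 6 sits in that position: it comes about two weeks before the nominal Week 29 scan and more than two months after the Week 17 scan.

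The error runs in one direction and is set by the calendar rather than by the treatment. Each combination is a single cohort with no concurrent control, so a 6-month PFS proportion is likely to be read against rates from elsewhere. Unless the reader knows which scans inform it, the figure will look like disease control through month 6 when much of the radiological evidence stops at Week 17.

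**Working it through.** The SAP states no PFS assumption or expected landmark value, so there is no figure of its own to reproduce. The check is calendar arithmetic followed by an illustration of size.

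**Inputs**
- Scan weeks 8, 17 and 29, each within 7 days (section 3.4).
- Weeks are anchored on Day 1. Section 3.1 has dosing "followed by intratumorally injections on Weeks 5, 8, 11, 17, 23, and 29 (Day 1 of Cycles 2 through 7"), so Week 29 is Day 1 of Cycle 7.
- Months = study day / 30.4375 (section 8.5).

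**Scan times**, with study day = 7 × (week − 1) + 1:

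| Scan | Day | Months | Window (months) |
|---|---|---|---|
| Week 8 | 50 | 1.64 | 1.41 to 1.87 |
| Week 17 | 113 | 3.71 | 3.48 to 3.94 |
| Week 29 | 197 | 6.47 | 6.24 to 6.70 |

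Month 6 is 6 × 30.4375 = day 182.6. The earliest permitted Week 29 scan is day 190, more than 7 days later. So no Week 29 scan done within its window can contribute an event by month 6.

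**Illustrative size at 6 months.** Assume exponential PFS with total hazard ln 2 / median. Split it into progression found only at scheduled scans (hazard lp) and deaths dated exactly (hazard ld). Then
- true PFS = exp(−(lp + ld) × 6)
- reported PFS = exp(−lp × 3.71) × exp(−ld × 6)

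The medians and the 30% death share are assumptions, not SAP figures.

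| Median (months) | True | Reported, all events scan-detected | Reported, 30% of events are deaths |
|---|---|---|---|
| 3 | 25.0% | 42.4% (+17.4) | 36.2% (+11.2) |
| 4 | 35.4% | 52.6% (+17.2) | 46.7% (+11.3) |
| 6 | 50.0% | 65.1% (+15.1) | 60.2% (+10.2) |
| 9 | 63.0% | 75.1% (+12.1) | 71.3% (+8.3) |
| 12 | 70.7% | 80.7% (+10.0) | 77.6% (+6.9) |

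**12 months (day 365.25).** The position depends on how the follow-up interval is applied:
- 13-week steps from Week 29: scans at 9.46 and 12.45 months.
- 12-week steps from Week 29: 9.23 and 11.99 months.
- 13-week steps from Week 32: 10.15 and 13.14 months.

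The last scan before month 12 may therefore fall anywhere from about 9.5 to 12.0 months. If it falls at 9.46 months, the same model gives +5.0, +8.5 and +7.9 points for medians of 3, 6 and 12 months with all events scan-detected, and +3.2, +5.7 and +5.4 with 30% deaths. If it falls at 11.99 months, the bias is close to nil.

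**Would a 7-month landmark help?** The Week 29 window closes at 6.70 months, so a 7-month estimate includes that scan. In the all-scan-detected case it reports 2^(−6.47/median) against a true 2^(−7/median):
- median 3: 22.4% vs 19.8%, +2.6 points
- median 6: 47.3% vs 44.5%, +2.8 points
- median 12: 68.8% vs 66.7%, +2.1 points

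The residual is 2 to 3 points, compared with 10 to 17 at month 6.

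**The case against.** A reader might infer that the 6-month figure is simply Week 17 PFS under a later label. The SAP does not support that. Several routes can add events between Week 17 and month 6:
- Deaths from any cause count on their own dates (section 8.5).
- The Phase 2 table has a directed physical at Week 23 (day 155, 5.09 months) that includes melanoma lesions. Appendix C allows caliper measurement of superficial lesions and treats a new unequivocal malignant lesion as progression.
- A response first seen at Week 17 calls for a confirmatory scan at least 4 weeks later, which can fall inside the gap.
- Subjects who stop treatment before progression leave the Week 17/29 grid. Someone stopping at Week 11 would be scanned by about 5.3 months if the follow-up clock starts then.

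All of this stands and reduces the bias, but none of it removes it. A subject still on treatment with stable disease at Week 17 gets no confirmatory scan. The formal response assessment is scheduled only at Weeks 8, 17 and 29. Appendix C also says that stopping treatment without objective evidence is not to be recorded as progression, so clinical decline alone does not fill the gap.

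A reader might also infer that the 12-month value rests on a scan at about Week 42, with the next at about Week 55. That is only one reading: the SAP sets a maximum interval and no start for the clock.

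Finally, PFS here is secondary and descriptive, and the SAP names no external PFS benchmark. Outside rates may carry similar detection delay, so the net error in any comparison cannot be known from this document. That limits the consequence but does not change the direction of the bias in the estimate itself.

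**Conclusion.** The 6-month point holds. For subjects on the treatment schedule, no scheduled scan falls between Week 17 (3.94 months at the latest) and month 6, because Week 29 cannot come before 6.24 months. With documentation dating and plain Kaplan-Meier, the 6-month PFS estimate is biased upward.

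The size is illustrative: about 7 to 11 points with 30% exactly dated deaths, and about 10 to 17 points if every event is scan-detected, over assumed medians of 3 to 12 months. The upper range is an extreme case. Neither range credits Week 23 examinations, confirmatory scans or off-schedule follow-up, so the actual bias may be smaller.

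The 12-month value is affected only conditionally, according to where the follow-up scans fall. The matter concerns what the PFS landmarks can support; the ORR tests and the two-stage design are untouched.

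**What to change.** Leave the scan calendar and the 6- and 12-month estimates as they are, and amend section 9.3.2 as follows:

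1. Add a Kaplan-Meier PFS estimate at 7 months, after the Week 29 window has closed at 6.70 months.
2. Footnote the 6-month value as carrying no scheduled on-treatment scan after Week 17.
3. Footnote the 12-month value as dependent on the actual follow-up scan dates.
4. Optionally, add an interval-censored sensitivity analysis and report it as bounds on 6-month PFS. For on-schedule subjects, month 6 lies between a last clear scan by day 120 and a progression scan from day 190. A nonparametric estimator such as Turnbull's cannot say how events are spread inside that interval, so it gives no corrected point estimate.

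A 13-month landmark should not replace the 12-month one. Section 3.2.2 ends the study about 1 year after the last Phase 2 subject starts, so late enrollees will not reach month 13. With a follow-up clock from Week 32 the scan would fall at 13.14 months and be missed anyway.

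The cost is SAP wording and one extra estimate from data already collected, plus the optional analysis. No visits are added. The 7-month figure will look less favourable than the 6-month one.
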